### **17.4.1.3. Chronic Lung Disease**

#### **17.4.1.3.1. ICD-10-CM Codes**

P27.0	Wilson-Mikity syndrome
P27.1	Bronchopulmonary dysplasia originating in the perinatal period
P27.8	Other chronic respiratory diseases originating in the perinatal period
P27.9	Unspecified chronic respiratory disease originating in the perinatal period
E84.0	Cystic fibrosis with pulmonary manifestations
E84.11	Meconium ileus in cystic fibrosis

- E84.19 Cystic fibrosis with other intestinal manifestations
- E84.8 Cystic fibrosis with other manifestations
- E84.9 Cystic fibrosis, unspecified
- I27.0 Primary pulmonary hypertension
- I27.1 Kyphoscoliotic heart disease
- I27.20 Pulmonary hypertension, unspecified
- I27.21 Secondary pulmonary arterial hypertension
- I27.22 Pulmonary hypertension due to left heart disease
- I27.23 Pulmonary hypertension due to lung diseases and hypoxia
- I27.24 Chronic thromboembolic pulmonary hypertension
- I27.29 Other secondary pulmonary hypertension
- I27.81 Cor pulmonale (chronic)
- I27.82 Chronic pulmonary embolism
- I27.83 Eisenmenger's syndrome
- I27.89 Other specified pulmonary heart diseases
- I27.9 Pulmonary heart disease, unspecified
- I28.0 Arteriovenous fistula of pulmonary vessels
- I28.1 Aneurysm of pulmonary artery
- I28.8 Other diseases of pulmonary vessels
- I28.9 Disease of pulmonary vessels, unspecified
- J41 Simple and mucopurulent chronic bronchitis
- J41.0 Simple chronic bronchitis
- J41.1 Mucopurulent chronic bronchitis
- J41.8 Mixed simple and mucopurulent chronic bronchitis

J42	Unspecified chronic bronchitis
J43.0	Unilateral pulmonary emphysema [MacLeod's syndrome]
J43.1	Panlobular emphysema
J43.2	Centrilobular emphysema
J43.8	Other emphysema
J43.9	Emphysema, unspecified
J44.0	Chronic obstructive pulmonary disease with (acute) lower respiratory infection
J44.1	Chronic obstructive pulmonary disease with (acute) exacerbation
J44.81	Bronchiolitis obliterans and bronchiolitis obliterans syndrome
J44.89	Other specified chronic obstructive pulmonary disease
J44.9	Chronic obstructive pulmonary disease, unspecified
J60	Coal worker's pneumoconiosis
J61	Pneumoconiosis due to asbestos and other mineral fibers
J62.0	Pneumoconiosis due to talc dust
J62.8	Pneumoconiosis due to other dust containing silica
J63.0	Aluminosis (of lung)
J63.1	Bauxite fibrosis (of lung)
J63.2	Berylliosis
J63.3	Graphite fibrosis (of lung)
J63.4	Siderosis
J63.5	Stannosis
J63.6	Pneumoconiosis due to other specified inorganic dusts
J64	Unspecified pneumoconiosis
J65	Pneumoconiosis associated with tuberculosis

J66.0	Byssinosis
J66.1	Flax-dressers' disease
J66.2	Cannabinosis
J66.8	Airway disease due to other specific organic dusts
J67	Hypersensitivity pneumonitis due to organic dust
J67.0	Farmer's lung
J67.1	Bagassosis
J67.2	Bird fancier's lung
J67.3	Suberosis
J67.4	Maltworker's lung
J67.5	Mushroom-worker's lung
J67.6	Maple-bark-stripper's lung
J67.7	Air conditioner and humidifier lung
J67.8	Hypersensitivity pneumonitis due to other organic dusts
J67.9	Hypersensitivity pneumonitis due to unspecified organic dust
J68.4	Chronic respiratory conditions due to chemicals, gases, fumes and vapors
J68.8	Other respiratory conditions due to chemicals, gases, fumes and vapors
J68.9	Unspecified respiratory condition due to chemicals, gases, fumes and vapors
J70.1	Chronic and other pulmonary manifestations due to radiation
J70.3	Chronic drug-induced interstitial lung disorders
J70.5	Respiratory conditions due to smoke inhalation
J81.1	Chronic pulmonary edema
J82.81	Chronic eosinophilic pneumonia

- J84.01 Alveolar proteinosis
- J84.02 Pulmonary alveolar microlithiasis
- J84.03 Idiopathic pulmonary hemosiderosis
- J84.09 Other alveolar and parieto-alveolar conditions
- J84.10 Pulmonary fibrosis, unspecified
- J84.111 Idiopathic interstitial pneumonia, not otherwise specified
- J84.112 Idiopathic pulmonary fibrosis
- J84.113 Idiopathic non-specific interstitial pneumonitis
- J84.115 Respiratory bronchiolitis interstitial lung disease
- J84.116 Cryptogenic organizing pneumonia
- J84.117 Desquamative interstitial pneumonia
- J84.170 Interstitial lung disease with progressive fibrotic phenotype in diseases classified elsewhere
- J84.178 Other interstitial pulmonary diseases with fibrosis in diseases classified elsewhere
- J84.2 Lymphoid interstitial pneumonia
- J84.81 Lymphangioleiomyomatosis
- J84.82 Adult pulmonary Langerhans cell histiocytosis
- J84.83 Surfactant mutations of the lung
- J84.841 Neuroendocrine cell hyperplasia of infancy
- J84.842 Pulmonary interstitial glycogenosis
- J84.843 Alveolar capillary dysplasia with vein misalignment
- J84.848 Other interstitial lung diseases of childhood
- J84.89 Other specified interstitial pulmonary diseases
- J84.9 Interstitial pulmonary disease, unspecified

Z77.090 Contact with and (suspected) exposure to asbestos

J85.0 Gangrene and necrosis of lung

J93.81 Chronic pneumothorax

#### **17.4.1.4. Down Syndrome**

##### **17.4.1.4.1. ICD-10-CM Codes**

Q90.0 Trisomy 21, nonmosaicism (meiotic nondisjunction)

Q90.1 Trisomy 21, mosaicism (mitotic nondisjunction)

Q90.2 Trisomy 21, translocation

Q90.9 Down syndrome, unspecified

#### **17.4.1.5. Heart Disease**

##### **17.4.1.5.1. ICD-10-CM Codes**

I01.0 Acute rheumatic pericarditis

I01.1 Acute rheumatic endocarditis

I01.2 Acute rheumatic myocarditis

I01.8 Other acute rheumatic heart disease

I01.9 Acute rheumatic heart disease, unspecified

I02.0 Rheumatic chorea with heart involvement

I05.0 Rheumatic mitral stenosis

I05.1 Rheumatic mitral insufficiency

I05.2 Rheumatic mitral stenosis with insufficiency

I05.8 Other rheumatic mitral valve diseases

I05.9 Rheumatic mitral valve disease, unspecified

I06.0 Rheumatic aortic stenosis

I06.1 Rheumatic aortic insufficiency

I06.2 Rheumatic aortic stenosis with insufficiency

- I07.0 Rheumatic tricuspid stenosis
- I07.1 Rheumatic tricuspid insufficiency
- I07.2 Rheumatic tricuspid stenosis and insufficiency
- I07.8 Other rheumatic tricuspid valve diseases
- I07.9 Rheumatic tricuspid valve disease, unspecified
- I06.8 Other rheumatic aortic valve diseases
- I06.9 Rheumatic aortic valve disease, unspecified
- I08.0 Rheumatic disorders of both mitral and aortic valves
- I08.1 Rheumatic disorders of both mitral and tricuspid valves
- I08.2 Rheumatic disorders of both aortic and tricuspid valves
- I08.3 Combined rheumatic disorders of mitral, aortic and tricuspid valves
- I08.8 Other rheumatic multiple valve diseases
- I08.9 Rheumatic multiple valve disease, unspecified
- I09.0 Rheumatic myocarditis
- I09.1 Rheumatic diseases of endocardium, valve unspecified
- I09.2 Chronic rheumatic pericarditis
- I09.81 Rheumatic heart failure
- I09.89 Other specified rheumatic heart diseases
- I09.9 Rheumatic heart disease, unspecified
- I11.0 Hypertensive heart disease with heart failure
- I11.9 Hypertensive heart disease without heart failure
- I13.0 Hypertensive heart and chronic kidney disease with heart failure and stage 1 through stage 4 chronic kidney disease, or unspecified chronic kidney disease

090177e1a5be86fe\Approved\Approved On: 19-Mar-2026 15:57 (GMT)

- I13.10 Hypertensive heart and chronic kidney disease without heart failure, with stage 1 through stage 4 chronic kidney disease, or unspecified chronic kidney disease
- I13.11 Hypertensive heart and chronic kidney disease without heart failure, with stage 5 chronic kidney disease, or end stage renal disease
- I13.2 Hypertensive heart and chronic kidney disease with heart failure and with stage 5 chronic kidney disease, or end stage renal disease
- I20.0 Unstable angina
- I20.1 Angina pectoris with documented spasm
- I20.8 Other forms of angina pectoris
- I21.01 ST elevation (STEMI) myocardial infarction involving left main coronary artery
- I21.02 ST elevation (STEMI) myocardial infarction involving left anterior descending coronary artery
- I21.09 ST elevation (STEMI) myocardial infarction involving other coronary artery of anterior wall
- I21.11 ST elevation (STEMI) myocardial infarction involving right coronary artery
- I21.19 ST elevation (STEMI) myocardial infarction involving other coronary artery of inferior wall
- I21.21 ST elevation (STEMI) myocardial infarction involving left circumflex coronary artery
- I21.29 ST elevation (STEMI) myocardial infarction involving other sites
- I21.3 ST elevation (STEMI) myocardial infarction of unspecified site
- I21.4 Non-ST elevation (NSTEMI) myocardial infarction
- I21.9 Acute myocardial infarction, unspecified
- I21.A1 Myocardial infarction type 2
- I21.A9 Other myocardial infarction type
- I22.0 Subsequent ST elevation (STEMI) myocardial infarction of anterior wall

090177e1a5be86fe\Approved\Approved On: 19-Mar-2026 15:57 (GMT)

- I22.1 Subsequent ST elevation (STEMI) myocardial infarction of inferior wall
- I22.2 Subsequent non-ST elevation (NSTEMI) myocardial infarction
- I22.8 Subsequent ST elevation (STEMI) myocardial infarction of other sites
- I22.9 Subsequent ST elevation (STEMI) myocardial infarction of unspecified site
- I23.0 Hemopericardium as current complication following acute myocardial infarction
- I23.1 Atrial septal defect as current complication following acute myocardial infarction
- I23.2 Ventricular septal defect as current complication following acute myocardial infarction
- I23.3 Rupture of cardiac wall without hemopericardium as current complication following acute myocardial infarction
- I23.4 Rupture of chordae tendineae as current complication following acute myocardial infarction
- I23.5 Rupture of papillary muscle as current complication following acute myocardial infarction
- I23.6 Thrombosis of atrium, auricular appendage, and ventricle as current complications following acute myocardial infarction
- I23.7 Postinfarction angina
- I23.8 Other current complications following acute myocardial infarction
- I24.0 Acute coronary thrombosis not resulting in myocardial infarction
- I24.1 Dressler's syndrome
- I24.8 Other forms of acute ischemic heart disease
- I24.9 Acute ischemic heart disease, unspecified
- I25.10 Atherosclerotic heart disease of native coronary artery without angina pectoris
- I25.110 Atherosclerotic heart disease of native coronary artery with unstable angina pectoris

- I25.111 Atherosclerotic heart disease of native coronary artery with angina pectoris with documented spasm
- I25.118 Atherosclerotic heart disease of native coronary artery with other forms of angina pectoris
- I25.119 Atherosclerotic heart disease of native coronary artery with unspecified angina pectoris
- I25.3 Aneurysm of heart
- I25.41 Coronary artery aneurysm
- I25.42 Coronary artery dissection
- I25.5 Ischemic cardiomyopathy
- I25.6 Silent myocardial ischemia
- I25.700 Atherosclerosis of coronary artery bypass graft(s), unspecified, with unstable angina pectoris
- I25.701 Atherosclerosis of coronary artery bypass graft(s), unspecified, with angina pectoris with documented spasm
- I25.708 Atherosclerosis of coronary artery bypass graft(s), unspecified, with other forms of angina pectoris
- I25.709 Atherosclerosis of coronary artery bypass graft(s), unspecified, with unspecified angina pectoris
- I25.710 Atherosclerosis of autologous vein coronary artery bypass graft(s) with unstable angina pectoris
- I25.711 Atherosclerosis of autologous vein coronary artery bypass graft(s) with angina pectoris with documented spasm
- I25.718 Atherosclerosis of autologous vein coronary artery bypass graft(s) with other forms of angina pectoris
- I25.719 Atherosclerosis of autologous vein coronary artery bypass graft(s) with unspecified angina pectoris
- I25.720 Atherosclerosis of autologous artery coronary artery bypass graft(s) with unstable angina pectoris
- I25.721 Atherosclerosis of autologous artery coronary artery bypass graft(s) with angina pectoris with documented spasm

- I25.728 Atherosclerosis of autologous artery coronary artery bypass graft(s) with other forms of angina pectoris
- I25.729 Atherosclerosis of autologous artery coronary artery bypass graft(s) with unspecified angina pectoris
- I25.730 Atherosclerosis of nonautologous biological coronary artery bypass graft(s) with unstable angina pectoris
- I25.731 Atherosclerosis of nonautologous biological coronary artery bypass graft(s) with angina pectoris with documented spasm
- I25.738 Atherosclerosis of nonautologous biological coronary artery bypass graft(s) with other forms of angina pectoris
- I25.739 Atherosclerosis of nonautologous biological coronary artery bypass graft(s) with unspecified angina pectoris
- I25.750 Atherosclerosis of native coronary artery of transplanted heart with unstable angina
- I25.751 Atherosclerosis of native coronary artery of transplanted heart with angina pectoris with documented spasm
- I25.758 Atherosclerosis of native coronary artery of transplanted heart with other forms of angina pectoris
- I25.759 Atherosclerosis of native coronary artery of transplanted heart with unspecified angina pectoris
- I25.760 Atherosclerosis of bypass graft of coronary artery of transplanted heart with unstable angina
- I25.761 Atherosclerosis of bypass graft of coronary artery of transplanted heart with angina pectoris with documented spasm
- I25.768 Atherosclerosis of bypass graft of coronary artery of transplanted heart with other forms of angina pectoris
- I25.769 Atherosclerosis of bypass graft of coronary artery of transplanted heart with unspecified angina pectoris
- I25.790 Atherosclerosis of other coronary artery bypass graft(s) with unstable angina pectoris
- I25.791 Atherosclerosis of other coronary artery bypass graft(s) with angina pectoris with documented spasm

090177e1a5be86fe\Approved\Approved On: 19-Mar-2026 15:57 (GMT)

- I25.798 Atherosclerosis of other coronary artery bypass graft(s) with other forms of angina pectoris
- I25.799 Atherosclerosis of other coronary artery bypass graft(s) with unspecified angina pectoris
- I25.810 Atherosclerosis of coronary artery bypass graft(s) without angina pectoris
- I25.811 Atherosclerosis of native coronary artery of transplanted heart without angina pectoris
- I25.812 Atherosclerosis of bypass graft of coronary artery of transplanted heart without angina pectoris
- I25.82 Chronic total occlusion of coronary artery
- I25.83 Coronary atherosclerosis due to lipid rich plaque
- I25.84 Coronary atherosclerosis due to calcified coronary lesion
- I25.89 Other forms of chronic ischemic heart disease
- I25.9 Chronic ischemic heart disease, unspecified
- I26.01 Septic pulmonary embolism with acute cor pulmonale
- I26.02 Saddle embolus of pulmonary artery with acute cor pulmonale
- I26.09 Other pulmonary embolism with acute cor pulmonale
- I27.1 Kyphoscoliotic heart disease
- I27.22 Pulmonary hypertension due to left heart disease
- I27.81 Cor pulmonale (chronic)
- I27.83 Eisenmenger's syndrome
- I27.9 Pulmonary heart disease, unspecified
- I30.0 Acute nonspecific idiopathic pericarditis
- I30.1 Infective pericarditis
- I30.8 Other forms of acute pericarditis
- I30.9 Acute pericarditis, unspecified

090177e1a5be86fe\Approved\Approved On: 19-Mar-2026 15:57 (GMT)

- I31.0 Chronic adhesive pericarditis
- I31.1 Chronic constrictive pericarditis
- I31.2 Hemopericardium, not elsewhere classified
- I31.3 Pericardial effusion (noninflammatory)
- I31.4 Cardiac tamponade
- I31.8 Other specified diseases of pericardium
- I31.9 Disease of pericardium, unspecified
- I33.0 Acute and subacute infective endocarditis
- I33.9 Acute and subacute endocarditis, unspecified
- I34.0 Nonrheumatic mitral (valve) insufficiency
- I34.1 Nonrheumatic mitral (valve) prolapse
- I34.2 Nonrheumatic mitral (valve) stenosis
- I34.8 Other nonrheumatic mitral valve disorders
- I34.9 Nonrheumatic mitral valve disorder, unspecified
- I35.0 Nonrheumatic aortic (valve) stenosis
- I35.1 Nonrheumatic aortic (valve) insufficiency
- I35.2 Nonrheumatic aortic (valve) stenosis with insufficiency
- I35.8 Other nonrheumatic aortic valve disorders
- I35.9 Nonrheumatic aortic valve disorder, unspecified
- I36.0 Nonrheumatic tricuspid (valve) stenosis
- I36.1 Nonrheumatic tricuspid (valve) insufficiency
- I36.2 Nonrheumatic tricuspid (valve) stenosis with insufficiency
- I36.8 Other nonrheumatic tricuspid valve disorders
- I36.9 Nonrheumatic tricuspid valve disorder, unspecified

090177e1a5be86fe\Approved\Approved On: 19-Mar-2026 15:57 (GMT)

- I37.0 Nonrheumatic pulmonary valve stenosis
- I37.1 Nonrheumatic pulmonary valve insufficiency
- I37.2 Nonrheumatic pulmonary valve stenosis with insufficiency
- I37.8 Other nonrheumatic pulmonary valve disorders
- I37.9 Nonrheumatic pulmonary valve disorder, unspecified
- I38 Endocarditis, valve unspecified
- I39 Endocarditis and heart valve disorders in diseases classified elsewhere
- I40.0 Infective myocarditis
- I40.1 Isolated myocarditis
- I40.8 Other acute myocarditis
- I40.9 Acute myocarditis, unspecified
- I41 Myocarditis in diseases classified elsewhere
- I42.0 Dilated cardiomyopathy
- I42.1 Obstructive hypertrophic cardiomyopathy
- I42.2 Other hypertrophic cardiomyopathy
- I42.3 Endomyocardial (eosinophilic) disease
- I42.4 Endocardial fibroelastosis
- I42.5 Other restrictive cardiomyopathy
- I42.6 Alcoholic cardiomyopathy
- I42.7 Cardiomyopathy due to drug and external agent
- I42.8 Other cardiomyopathies
- I42.9 Cardiomyopathy, unspecified
- I43 Cardiomyopathy in diseases classified elsewhere
- I44.0 Atrioventricular block, first degree

- I44.1 Atrioventricular block, second degree
- I44.2 Atrioventricular block, complete
- I44.3 Other and unspecified atrioventricular block
- I44.30 Unspecified atrioventricular block
- I44.39 Other atrioventricular block
- I44.4 Left anterior fascicular block
- I44.5 Left posterior fascicular block
- I44.60 Unspecified fascicular block
- I44.69 Other fascicular block
- I44.7 Left bundle-branch block, unspecified
- I45.0 Right fascicular block
- I45.10 Unspecified right bundle-branch block
- I45.19 Other right bundle-branch block
- I45.2 Bifascicular block
- I45.3 Trifascicular block
- I45.4 Nonspecific intraventricular block
- I45.5 Other specified heart block
- I45.6 Pre-excitation syndrome
- I45.81 Long QT syndrome
- I45.89 Other specified conduction disorders
- I45.9 Conduction disorder, unspecified
- I46.2 Cardiac arrest due to underlying cardiac condition
- I46.8 Cardiac arrest due to other underlying condition
- I46.9 Cardiac arrest, cause unspecified

- I47.0 Re-entry ventricular arrhythmia
- I47.1 Supraventricular tachycardia
- I47.2 Ventricular tachycardia
- I47.9 Paroxysmal tachycardia, unspecified
- I48.0 Paroxysmal atrial fibrillation
- I48.11 Longstanding persistent atrial fibrillation
- I48.19 Other persistent atrial fibrillation
- I48.20 Chronic atrial fibrillation, unspecified
- I48.21 Permanent atrial fibrillation
- I48.3 Typical atrial flutter
- I48.4 Atypical atrial flutter
- I48.91 Unspecified atrial fibrillation
- I48.92 Unspecified atrial flutter
- I49.01 Ventricular fibrillation
- I49.02 Ventricular flutter
- I49.1 Atrial premature depolarization
- I49.2 Junctional premature depolarization
- I49.3 Ventricular premature depolarization
- I49.40 Unspecified premature depolarization
- I49.49 Other premature depolarization
- I49.5 Sick sinus syndrome
- I49.8 Other specified cardiac arrhythmias
- I49.9 Cardiac arrhythmia, unspecified
- I50.1 Left ventricular failure, unspecified

090177e1a5be86fe\Approved\Approved On: 19-Mar-2026 15:57 (GMT)

- I50.21 Acute systolic (congestive) heart failure
- I50.22 Chronic systolic (congestive) heart failure
- I50.23 Acute on chronic systolic (congestive) heart failure
- I50.30 Unspecified diastolic (congestive) heart failure
- I50.31 Acute diastolic (congestive) heart failure
- I50.32 Chronic diastolic (congestive) heart failure
- I50.33 Acute on chronic diastolic (congestive) heart failure
- I50.40 Unspecified combined systolic (congestive) and diastolic (congestive) heart failure
- I50.41 Acute combined systolic (congestive) and diastolic (congestive) heart failure
- I50.42 Chronic combined systolic (congestive) and diastolic (congestive) heart failure
- I50.43 Acute on chronic combined systolic (congestive) and diastolic (congestive) heart failure
- I50.810 Right heart failure, unspecified
- I50.811 Acute right heart failure
- I50.812 Chronic right heart failure
- I50.813 Acute on chronic right heart failure
- I50.814 Right heart failure due to left heart failure
- I50.82 Biventricular heart failure
- I50.83 High output heart failure
- I50.84 End stage heart failure
- I50.89 Other heart failure
- I50.9 Heart failure, unspecified
- I51.0 Cardiac septal defect, acquired

090177e1a5be86fe\Approved\Approved On: 19-Mar-2026 15:57 (GMT)

- I51.1 Rupture of chordae tendineae, not elsewhere classified
- I51.2 Rupture of papillary muscle, not elsewhere classified
- I51.3 Intracardiac thrombosis, not elsewhere classified
- I51.4 Myocarditis, unspecified
- I51.5 Myocardial degeneration
- I51.7 Cardiomegaly
- I51.81 Takotsubo syndrome
- I51.89 Other ill-defined heart diseases
- I51.9 Heart disease, unspecified
- I52 Other heart disorders in diseases classified elsewhere

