### 9.3.3. Covariates

All members of the study cohorts will be described according to covariates identified in the claims data. Demographic attributes will be determined on the vaccination/cohort entry date, while other factors will be assessed in the one year prior to the cohort entry date. Unless specified as for descriptive purposes only, the covariates listed will be included in the PS models. All variables are binary unless otherwise specified.

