$$\begin{aligned} & \text{logit}\{P(T_i = 1 \mid \mathbf{X}_i)\} \\ &= \beta_0 + \beta_1 \text{Sex (binary)}_i + \beta_2 \text{Age (categorical)}_i \\ &+ \beta_3 \text{Calendar month (categorical)}_i + \beta_4 \text{Geographic region (categorical)}_i \\ &+ \beta_5 \text{Asthma (binary)}_i + \beta_6 \text{Non-malignant blood disorders (binary)}_i \\ &+ \beta_7 \text{Chronic lung disease (binary)}_i + \beta_8 \text{Down syndrome (binary)}_i \\ &+ \beta_9 \text{Heart disease (binary)}_i \\ &+ \beta_{10} \text{History of SARS-CoV-2 infection (binary)}_i \\ &+ \beta_{11} \text{Immunocompromised status (binary)}_i \\ &+ \beta_{12} \text{Kidney disorders (binary)}_i + \beta_{13} \text{Liver disorders (binary)}_i \\ &+ \beta_{14} \text{Neurological or neurodevelopmental conditions (binary)}_i \\ &+ \beta_{15} \text{Malignant neoplasms (binary)}_i + \beta_{16} \text{Obesity (binary)}_i \\ &+ \beta_{17} \text{Type II diabetes (binary)}_i \\ &+ \beta_{18} \text{Number of hospitalizations in prior year (continuous)}_i \\ &+ \beta_{19} \text{Number of emergency room visits in prior year (continuous)}_i \\ &+ \beta_{20} \text{Number of outpatient encounters in prior year (continuous)}_i \\ &+ \beta_{21} \text{Seasonal influenza vaccination (binary)}_i \\ &+ \beta_{22} \text{RSV vaccination (binary)}_i + \beta_{23} \text{Systemic immunomodulators (binary)}_i \\ &+ \beta_{24} \text{Oral corticosteroids (binary)}_i + \beta_{25} \text{Antivirals (binary)}_i \\ &+ \beta_{26} \text{Antibiotics (binary)}_i + \beta_{27} \text{Identified empiric variables (binary)}_i, \end{aligned}$$

where  $T_i$  denotes exposure status for individual  $i$ , with  $T_i = 1$  indicating a recorded vaccination of the COMIRNATY 2023-2024 Formula and  $T_i = 0$  indicating no recorded vaccination of the COMIRNATY 2023-2024 Formula.

A greedy digit-based matching algorithm will be used, in which patients exposed to the COMIRNATY 2023-2024 Formula are matched without replacement to comparator patients at a given level of precision defined by the number of digits of the PS (Parsons, 2001), to a maximum of 8 decimal places. When no further matches are available at a given level of precision, the number of digits is sequentially reduced until a maximum allowable caliper of 0.1 is reached, thereby ensuring that the matched cohorts are comparable with respect to the underlying measured risk factors. Matching by propensity score will be conducted within

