strata defined by age group and calendar period. A matching ratio (e.g., up to 1:10) may be implemented.

PS matching will produce a single matched cohort (the master cohort) that will be used to conduct all primary, secondary, and sub-group analyses for the study outcomes. Balance between the PS-matched cohorts will be evaluated by overlaying graphs of the PS distributions in COMIRNATY-exposed and comparator cohorts before and after PS matching. Additionally, standardized differences between the PS-matched cohorts for each covariate in the model will also be assessed. Variables with an absolute standardized difference less than 0.1 will be considered balanced (Austin, 2009). If a variable has a standardized difference that is greater than 0.1, further PS model modifications (e.g., addition of interaction terms) or inclusion of the imbalanced covariates in an outcome model will be considered (Normand et al., 2001). If there are confounders identified that would only be appropriate to include for one outcome and not the others, a separate PS model for the specific outcome will be considered.

Outcome-specific exclusion criteria will be applied to the master cohort after PS matching but before the outcome specific analysis; the matched cohort that remains will be the analytic cohort for that specific outcome. The matched comparators of individuals excluded for outcome-specific exclusion criteria will also be excluded from the outcome-specific analysis.

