D61.89	Other specified aplastic anemias and other bone marrow failure syndromes
D61.9	Aplastic anemia, unspecified
D62	Acute posthemorrhagic anemia
D63.0	Anemia in neoplastic disease
D63.1	Anemia in chronic kidney disease
D63.8	Anemia in other chronic diseases classified elsewhere
D64.0	Hereditary sideroblastic anemia
D64.1	Secondary sideroblastic anemia due to disease
D64.2	Secondary sideroblastic anemia due to drugs and toxins
D64.3	Other sideroblastic anemias
D64.4	Congenital dyserythropoietic anemia
D64.81	Anemia due to antineoplastic chemotherapy
D64.89	Other specified anemias
D64.9	Anemia, unspecified
D65	Disseminated intravascular coagulation
D66	Hereditary factor VIII deficiency
D67	Hereditary factor IX deficiency
D68.00	Von Willebrand disease, unspecified
D68.1	Hereditary factor XI deficiency
D68.01	Von Willebrand disease, type 1
D68.020	Von Willebrand disease, type 2A
D68.021	Von Willebrand disease, type 2B

D68.022	Von Willebrand disease, type 2M
D68.023	Von Willebrand disease, type 2N
D68.029	Von Willebrand disease, type 2, unspecified
D68.03	Von Willebrand disease, type 3
D68.04	Acquired von Willebrand disease
D68.09	Other von Willebrand disease
D68.1	Hereditary factor XI deficiency
D68.2	Hereditary deficiency of other clotting factors
D68.311	Acquired hemophilia
D68.312	Antiphospholipid antibody with hemorrhagic disorder
D68.318	Other hemorrhagic disorder due to intrinsic circulating anticoagulants, antibodies, or inhibitors
D68.32	Hemorrhagic disorder due to extrinsic circulating anticoagulants
D68.4	Acquired coagulation factor deficiency
D68.51	Activated protein C resistance
D68.52	Prothrombin gene mutation
D68.59	Other primary thrombophilia
D68.61	Antiphospholipid syndrome
D68.62	Lupus anticoagulant syndrome
D68.69	Other thrombophilia
D68.8	Other specified coagulation defects
D68.9	Coagulation defect, unspecified
D69.0	Allergic purpura
D69.1	Qualitative platelet defects

D69.2	Other nonthrombocytopenic purpura
D69.3	Immune thrombocytopenic purpura
D69.41	Evans syndrome
D69.42	Congenital and hereditary thrombocytopenia purpura
D69.49	Other primary thrombocytopenia
D69.51	Post-transfusion purpura
D69.59	Other secondary thrombocytopenia
D69.6	Thrombocytopenia, unspecified
D69.8	Other specified hemorrhagic conditions
D69.9	Hemorrhagic condition, unspecified
D70.0	Congenital agranulocytosis
D70.1	Agranulocytosis secondary to cancer chemotherapy
D70.2	Other drug-induced agranulocytosis
D70.3	Neutropenia due to infection
D70.4	Cyclic neutropenia

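### In the Phase 2 cohort, heart disease and non-malignant blood disorders each enter the propensity score as one yes/no term, so a high-risk component can stay unbalanced while the composite reads balanced

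*Protocol*

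**What the plan says.** Section 9.3.3 sets the default form of the covariates: "All variables are binary unless otherwise specified". The PS equation in 9.7.2.1 then carries "Heart disease (binary" and "Non-malignant blood disorders (binary" as one coefficient each.

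The code lists behind those two flags are wide.

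- **Heart disease (17.4.1.5.1)** runs from "I44.0 Atrioventricular block, first degree" through "I48.91 Unspecified atrial fibrillation" to end-stage heart failure (I50.84). Ischemic disease, valve disease, cardiomyopathy, premature beats and cardiomegaly are also included.
- **Non-malignant blood disorders (17.4.1.2.1)** put "Activated protein C resistance" and other thrombophilias under the same flag as hereditary factor VIII deficiency, D64.9 (anemia not further specified) and abnormal white-cell counts.

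On balance, 9.7.2.1 states that "standardized differences between the PS-matched cohorts for each covariate in the model will also be assessed", with an absolute value below 0.1 taken as balanced. Under 9.7.2.2, covariates found imbalanced go into the Poisson outcome model. One matched master cohort serves the primary, secondary and subgroup analyses.

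**The concern.** Myocardial infarction (MI), both stroke types, pulmonary embolism (PE) and cerebral venous sinus thrombosis (CVST) are study outcomes. The pooled conditions relate to them very differently. Heart failure and first-degree AV block do not carry the same risk, and clotting and bleeding disorders plausibly act in opposite directions.

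Matching on a PS that contains only the pooled flag aims to balance that flag, not what lies inside it. A component that is not a model term has no row in the planned balance assessment. It therefore cannot trigger the 0.1 rule or the outcome-model adjustment. If the severe share of the composite differs between recipients and matched comparators, the cardiovascular and thrombotic rate ratios shift, and the planned diagnostics for these two terms would not show it.

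**Working it through.** The protocol states no component prevalences, vaccination patterns or risk ratios, so there is no plan figure to reproduce. **Every input below is an assumption.** The check asks whether a balanced composite can hide an imbalance, and how large the effect would be.

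**1. Closed form, heart disease, conditioning on the composite alone.**

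Inputs: severe 20%, minor 20%, none 60%. Vaccination probability is 0.25 without heart disease, with log-odds shifts b_s (severe) and b_m (minor). Outcome risk ratio is 3 or 6 for severe and 1.2 for minor, against none.

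Formulas:
- p = expit(ln(0.25/0.75) + b).
- Comparators are re-weighted to the recipients' composite prevalence.
- SMD = (p1 − p0) / √[(p1(1−p1) + p0(1−p0))/2].
- Null rate ratio = mean risk in recipients / mean risk in comparators.

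Worked case, b_s = −0.3 and b_m = +0.3:
- p_s = 0.198, p_m = 0.310. Overall vaccinated = 0.20×0.198 + 0.20×0.310 + 0.60×0.25 = 0.252.
- Recipients: severe 15.7%, minor 24.7%, composite 40.4%.
- Comparators before re-weighting: severe 21.4%, minor 18.4%, composite 39.9%. After re-weighting to 40.4%: severe 21.7%, minor 18.7%. The composite SMD is 0 by construction.
- SMD for severe disease = (0.157 − 0.217)/0.389 = −0.15.
- Null rate ratio at risk ratio 6 = (0.596 + 6×0.1574 + 1.2×0.2466) / (0.596 + 6×0.2172 + 1.2×0.1868) = 1.836/2.123 = 0.865.

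| b_s / b_m | Severe, recipients v comparators | SMD severe | Null rate ratio (risk ratio 3; 6) |
|---|---|---|---|
| −0.1 / +0.1 | 18.5% v 20.5% | −0.05 | 0.975; 0.954 |
| −0.2 / +0.2 | 17.1% v 21.1% | −0.10 | 0.951; 0.908 |
| −0.3 / +0.3 | 15.7% v 21.7% | −0.15 | 0.927; 0.865 |
| −0.3 / −0.1 | 16.8% v 18.6% | −0.05 | 0.977; 0.956 |
| −0.3 / −0.3, or +0.1 / +0.1 | equal | 0.00 | 1.000; 1.000 |
| +0.3 / +0.1 | 23.3% v 21.2% | +0.05 | 1.027; 1.050 |
| +0.3 / −0.3 | 24.7% v 18.7% | +0.15 | 1.076; 1.145 |

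**2. Blood disorders, same method.** Assume a composite of 15% in both groups, thrombophilia 5% v 15% of it, risk ratio 1.2 for other blood disorders and ten times that for thrombophilia.
- Thrombophilia is 0.75% v 2.25% overall, SMD −0.124.
- Null rate ratio = (0.85 + 0.1425×1.2 + 0.0075×12) / (0.85 + 0.1275×1.2 + 0.0225×12) = 1.111/1.273 = 0.873.
- Over composites of 8% to 15%, several splits in both directions and thrombophilia risk ratios of 3 to 10, the absolute SMD is 0.040 to 0.124 and the null rate ratio 0.873 to 1.045.

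**3. Do utilization counts repair it?** Simulation of 400,000 people: heart disease 20%, a quarter of it heart failure; risk ratio 1.5 for heart disease and a further 4 for heart failure; weighting to the treated as a stand-in for matching. The log-odds shift for heart failure is on top of +0.3 for any heart disease.

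| PS contents | Heart failure shift −0.7: SMD; null rate ratio | Heart failure shift +0.5: SMD; null rate ratio |
|---|---|---|
| Composite only | −0.122; 0.915 | 0.098; 1.081 |
| + hospitalization and outpatient counts | −0.097; 0.933 | 0.078; 1.064 |
| + separate heart failure flag | 0.000; 1.000 | 0.000; 1.000 |

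The counts removed about one fifth of the imbalance: (0.122 − 0.097)/0.122 = 20%. The composite's own SMD never exceeded 0.001.

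**The case against.** The protocol has several partial safeguards.

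- **Empiric covariates (9.3.3).** The 25 most frequent diagnoses, drugs and procedures are examined, and potential confounders may enter the PS. A common code such as atrial fibrillation, or a drug that marks it, could then be modeled and checked for balance. A reader might infer that component imbalance can never be seen; this step shows that is too strong. But it is ranked by frequency and discretionary, so it is weakest for rare, high-risk conditions such as thrombophilia.
- **Other PS terms.** Hospitalization, emergency and outpatient counts, kidney disease, diabetes, obesity and chronic lung disease are separate terms. The closed form ignores them, so its range is not what the full model would leave.
- **Outcome-specific PS (9.7.2.1).** It may be considered, but no trigger is tied to composite content.
- **Clean periods (Table 2).** For MI, PE, both strokes and CVST they remove people with the same outcome in the prior 365 days. They do not remove heart failure, atrial fibrillation or thrombophilia.
- **A second design.** These outcomes are also analyzed in the self-controlled risk interval design, which is not exposed to time-fixed comorbidity.

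A reader might also infer that the bias hides harm. The documents do not support a direction: that result needs severe disease to lower vaccination relative to minor disease, equal shifts give no bias, and the reverse skew gives a rate ratio above 1. Nor do they show that the expectation in 9.7.2.1 of minimal residual confounding fails for these outcomes. They show only that the planned check would not reveal a failure inside these composites.

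**Conclusion.** The point stands as a weakness of specification confined to the Phase 2 cohort. Two broad composites are fixed as single PS terms, the balance rule covers only model terms, and no safeguard requires a look inside a composite. Whether imbalance will occur, and in which direction, cannot be read from the protocol.

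Under the assumptions shown, the opposite-sign scenarios give a null rate ratio of 0.98 to 0.87. The milder reverse skews give 1.03 to 1.08, and the exact mirror of the strongest scenario 1.08 to 1.15. A wider grid reached 0.72, but only with heart disease at 35%, a severe share of 20% v 40%, and an eightfold severe-to-mild risk ratio. These shifts are small beside the signal definition of a rate ratio above 3.0 in 9.3.2. They could still blur moderate effects on MI, stroke or PE, and the Phase 2 rate ratios will be read as estimates in their own right.

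**What to change.** In 9.3.3 and the PS equation, replace the two composites with separate binary terms cut from the existing lists.

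- **Heart:** ischemic heart disease (I20–I25); heart failure (I50, I11.0, I13.0, I13.2, I09.81); atrial fibrillation/flutter (I48); valve disease (I05–I08, I34–I39); cardiomyopathy, myocardial or pericardial disease (I30–I31, I40–I43); other.
- **Blood:** thrombophilia (D68.5x–D68.6x); coagulation and platelet disorders (D65–D68.4, D69); hemoglobinopathy and hemolytic anemia (D55–D59); other.

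Apply the 0.1 rule to each term. Ten terms replace two, so the model gains eight, all from codes already listed. The real cost is re-running the PS and the matching, because one master cohort feeds every Phase 2 analysis.

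Version 3.0 is dated 18 March 2026 and the final report is planned for 30 April 2026, so a re-match may not be feasible. In that case, add the same components as rows in the matched-cohort balance table. Put any with an absolute standardized difference above 0.1 into the Poisson model under 9.7.2.2. That costs only the extra rows and any resulting outcome-model terms.
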